	
than < 11 seconds in duration.
 
One healthy volunteer subject had two separate arrhythmic events which consisted of a single episode of atrial tachycardia 10 minutes after administration of GSK3039294 - when neither prodrug or CPHPC were detectable - followed by a single 5-beat episode of AIVR approximately 12 hours later.
	
Subjects will be withdrawn from the study if the Investigator deems any cardiac AE to be clinically concerning, and / or triggers the measurement of plasma hs-cTn to exclude the possibility of arrhythmia-associated myocardial ischemia / injury (see Section 5.4.4. & Section 7.3.7.).

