5.4.3. QTc Stopping Criteria

Healthy Volunteers & Amyloidosis Patients:

A healthy volunteer or patient that meets either bulleted criterion below will be withdrawn from the study.

- QTcF > 500 msec,
- Change from baseline in healthy volunteer subjects: QTcF >60 msec

For patients with underlying **bundle branch block**, follow the discontinuation criteria listed below:

Baseline QTcF with Bundle Branch Block	Discontinuation QTcF with Bundle Branch Block
< 450 msec	> 500 msec
450 – 480 msec	≥ 530 msec

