5.4.4. Cardiac Arrhythmia Stopping Criteria

All cardiac arrhythmias in individual subjects will be reviewed by the Investigator in consultation with the Medical Monitor at the earliest possible opportunity after the event, and will also be reviewed by a cardiologist where it is deemed appropriate to do so by the Investigator in consultation with the Medical Monitor on a case-by-case basis.

A clinically concerning cardiac arrhythmia in this study is any type of arrhythmia or divergent QRS complex morphology that is deemed by the Investigator to be reasonably attributable to GSK3039294 - rather than within normal variation for each type of affected subject receiving repeat dose GSK3039294; i.e. healthy volunteer subjects in Part B, or systemic amyloidosis patients with known cardiac involvement Part C.

Furthermore, a clinically concerning arrhythmia is an adverse event which is deemed by the Investigator in consultation with the Medical Monitor to be of sufficient temporal duration and / or character to potentially affect subject safety.

Detection of the following during baseline assessment or following administration of GSK3039294 will lead to withdrawal:

- a).** Sustained (≥ 10 beats) / symptomatic monomorphic ventricular tachycardia (VT), or rapid polymorphic VT; **b).** Complete heart block; **c).** Brady arrhythmias deemed

clinically concerning by the Investigator in consultation with the Medical Monitor (i.e. *except* physiological bradycardia or first degree heart block).

[figure not shown]
Additional cardiac arrhythmic events could include, but are not restricted, to:

- A sustained arrhythmia (i.e. ≥ 30 seconds) *except* physiological bradycardia.
- A non-sustained wide-complex tachyarrhythmia ≥ 100 / minute that is:
 - accompanied by symptoms or other new ECG changes (e.g. new ST depression)
 - repetitive (e.g. repeated short salvos)
 - Greater than 10 seconds in duration

Subjects who either have a clinically concerning arrhythmic event during the study, or where there is electrophysiological diagnostic uncertainty on cardiac telemetry / ECG, must be withdrawn from the study, and should have an immediate cardiac troponin level evaluated using a high-sensitivity point-of-care assay as outlined in **Section 7.3.7** & **Figure 5**, below.

Affected subjects should be referred to the local cardiology service and the Medical Monitor should be informed as soon as possible.

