5.6. Subject and Study Completion

A completed subject is one who has completed all phases of the study including the final follow-up visit.

The end of the study is defined as the last subject's last visit.

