7.3.1.3. Follow-up of AEs and SAEs

After the initial AE/SAE report, the investigator is required to proactively follow each subject at subsequent visits/contacts. All SAEs, and non-serious AEs of special interest (as defined in Section 4.6.1) will be followed until resolution, until the condition stabilizes, until the event is otherwise explained, or until the subject is lost to follow-up (as defined in Section 5.4). Further information on follow-up procedures is given in [Appendix 4](#).

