7.3.4. Vital Signs

- Vital signs will be measured in semi-supine position after 5 minutes rest and will include temperature, systolic and diastolic blood pressure and pulse.
- Triplicate readings of blood pressure and pulse rate will be taken and averaged at all times.

7.3.5. Cardiac Monitoring – Electrocardiogram (ECG), Telemetry & Non-Implantable Devices for Remote Monitoring

- 12-lead ECGs will be measured in semi-supine position after 5 minutes rest (triplicate readings will be taken and averaged at all times) will be obtained at each timepoint during the study using an ECG machine that automatically calculates the heart rate and measures PR, QRS, QT, and QTcF intervals. Refer to Section [5.4.3](#) for QTcF withdrawal criteria and additional QTcF readings that may be necessary.

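### The QTcF stopping rule takes dosed subjects out of the study, not only off treatment, and the additional QTcF readings that 7.3.5 refers to are not in 5.4.3

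*Protocol*

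**What the plan says.** Section 5.4.3 of the protocol sets two QTcF limits: above 500 msec for anyone, and a rise of more than 60 msec from baseline for healthy volunteers. The consequence is that "A healthy volunteer or patient that meets either bulleted criterion below will be withdrawn from the study". A separate table for patients with bundle branch block gives discontinuation thresholds but does not say whether treatment or the study is discontinued.

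Section 5.6 ties follow-up to participation: "A completed subject is one who has completed all phases of the study including the final follow-up visit".

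Section 7.3.5 sends the reader to 5.4.3 "for QTcF withdrawal criteria and additional QTcF readings that may be necessary".

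The general adverse-event text says: "After the initial AE/SAE report, the investigator is required to proactively follow each subject at subsequent visits/contacts". It then sets a stronger duty for a narrower group: "All SAEs, and non-serious AEs of special interest (as defined in Section 4.6.1) will be followed until resolution", with stabilisation, another explanation or loss to follow-up as the other end points.

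The arrhythmia rule in 5.4.4 is worded like the QTcF rule. Affected subjects "must be withdrawn from the study, and should have an immediate cardiac troponin level evaluated using a high-sensitivity point-of-care assay". The mitigation cell in 4.6.1 says: "Subjects will be withdrawn from the study if the Investigator deems any cardiac AE to be clinically concerning".

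**The concern.** Stopping the drug and leaving the study are separate decisions, and 5.4.3 merges them. A subject whose QTcF crosses a limit must stop dosing. That subject is also the one whose later course is most informative. Safety is the primary objective of every part and there is no control group, so whether the interval returns to baseline off drug is useful evidence on causality for the Dose Escalation Committee. Read literally, the rule ends study participation when that question arises.

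In Part C the rule also leaves it unclear whether the patient attends the visits at which time to SAP repletion, part of a secondary endpoint, is measured. Replacing the subject, as 5.4 provides, restores the cohort size but not that person's recovery data.

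**Working it through.** The plan states no figure on this point, so the check compares sections and then counts visits.

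1. **What ends.** The main QTcF rule in 5.4.3 removes the subject from the study. Under 5.6 the final follow-up visit is a phase of the study. Taken together and read literally, the follow-up visit falls after the subject has left. The bundle branch block table does not settle the matter either way.

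2. **Is there a retention rule elsewhere?** The general withdrawal text in 5.4 has none, and the Time and Events tables in 7.1 contain no early-withdrawal visit. The follow-up windows are timed from the last dose (7–14 days for safety; up to 42 days for SAP in Part C), so they can be applied to an early stopper, but nothing says that they are.

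3. **Does adverse-event follow-up cover it?** Section 7.3.1.1 collects events until the follow-up contact, and the first sentence of 7.3.1.3 covers each subject. Section 12.4.4 asks for supplemental evaluations as indicated or as the sponsor requests. None of these names a visit or an ECG that a withdrawn subject must have. Section 7.3.1.1 also says that investigators need not actively look for events in former subjects.

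4. **Is QTcF on the follow-to-resolution list?** For non-serious events, 7.3.1.3 relies on 4.6.1. The cardiac entries there are the preclinical blood pressure, pulse pressure, heart rate and QA interval findings, and the Part A arrhythmias. QTcF prolongation is not an entry. A non-serious QTcF event therefore has no express duty of follow-up to resolution.

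5. **The cross-reference.** Section 7.3.5 expects additional QTcF readings in 5.4.3, which holds only thresholds. Section 5.4.1 asks for a triplicate average and itself refers on to 5.4.3. No visible text defines a repeat ECG after a QTcF stop.

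6. **Count of visits.**
   - Cohort 3, with a stop on Day 3 as an illustration: 7.1.2 schedules ECGs on Days 4, 5, 6, 7 and 8 and at follow-up, so 5 + 1 = 6. The Day 4–8 ECGs belong to the in-patient dosing course, and the table times them before and 1 hour after dosing. They have little purpose once dosing has stopped. That leaves 6 − 5 = 1, the follow-up visit ECG.
   - Part C: weekly SAP samples to 42 days after the last dose give 42 / 7 = 6. One safety follow-up sample makes up to 6 + 1 = 7 per patient.

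7. **Frequency.** The protocol gives no trigger rate. Its synopsis reports no QTcF prolongation in Part A after single doses of 200, 600 or 1200 mg. Part A did not test repeat dosing.

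**The case against.** The strongest reply is that this protocol does not use withdrawal from the study to mean that observation ends. In 5.4.2, Part C patients who meet the Table 6 limits are also withdrawn from the study, yet the section points to the follow-up assessments in Appendix 2. Cohort 4a subjects withdrawn after the Day 7 review are to be followed up (4.2.2.3). The arrhythmia rule orders troponin testing in the same sentence that withdraws the subject. In addition, 12.4.1 makes a clinically significant ECG abnormality an adverse event, 12.4.2 lets the investigator class an important medical event as serious, and 7.3 allows extra safety time points.

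Much of this stands. It shows that a careful site could, and probably would, keep watching the subject. It does not show that the protocol requires it. The Cohort 4a follow-up is at the investigator's discretion and per local practice, and the other provisions depend on judgement or on a request. It also limits the comparison with the liver rules: the patient half of Appendix 2 does separate stopping treatment from leaving the study, but Table 6 uses the same wording as 5.4.3.

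A reader might infer that the arrhythmia rule leaves an equal gap. The documents do not support that. Arrhythmias are listed in 4.6.1, so 7.3.1.3 follows them to resolution or stabilisation. Section 7.3.7 adds serial troponin and, at the investigator's discretion, serial ECGs and imaging. Section 7.3.5.2 allows longer monitoring in patients with cardiac amyloid. The management algorithm in Figure 5 is not shown and may add more.

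**Conclusion.** The point holds for the QTcF rule. Section 5.4.3 states a rule that, taken literally, removes dosed subjects before their scheduled follow-up. Non-serious QTcF prolongation has no express follow-up to resolution, and the reference in 7.3.5 leads to nothing. This should be corrected, but it is a modest defect.

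A reader might infer that six ECG days and seven SAP samples would be lost for each affected subject. That is too strong. The visits are not expressly required, and a site may still hold them. Only one of the six Cohort 3 ECG days is worth retaining. The Part C samples, up to seven, would come from a patient who had not received the full 21-day regimen, so they are supplementary for SAP repletion and do not answer the QTcF question.

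The conclusion rests on three assumptions: the subject consents to stay, no follow-up rule for QTcF lies in the figure that is not shown (its title limits it to arrhythmia), and the trigger is rare. The last is likely from Part A but untested under repeat dosing.

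**What to change.** For subjects who have received at least one dose:

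- Change the consequence in 5.4.3 to permanent discontinuation of study treatment, and apply the same consequence to the bundle branch block table.
- State that consenting subjects complete the existing safety follow-up visit 7–14 days after the last dose and, in Part C, the weekly PD visits.
- Add to 5.4.3 repeat triplicate ECGs until QTcF returns to baseline or stabilises. This supplies the readings that 7.3.5 refers to and gives QTcF stopping events a defined end point for follow-up.
- Align the wording of 5.4.4 and the 4.6.1 cell, for consistency only. Section 5.4.4 covers two situations: "Detection of the following during baseline assessment or following administration of GSK3039294 will lead to withdrawal". Keep study withdrawal for arrhythmias found before dosing.

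None of this changes when dosing stops. The cost is an amendment plus a few unscheduled ECGs and some visits by subjects no longer on drug. The follow-up visits already exist in the schedule, but the repeat ECGs to recovery would be new assessments, so the change is cheap but goes beyond wording.

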5.4.4. Cardiac Arrhythmia Stopping Criteria

All cardiac arrhythmias in individual subjects will be reviewed by the Investigator in consultation with the Medical Monitor at the earliest possible opportunity after the event, and will also be reviewed by a cardiologist where it is deemed appropriate to do so by the Investigator in consultation with the Medical Monitor on a case-by-case basis.

A clinically concerning cardiac arrhythmia in this study is any type of arrhythmia or divergent QRS complex morphology that is deemed by the Investigator to be reasonably attributable to GSK3039294 - rather than within normal variation for each type of affected subject receiving repeat dose GSK3039294; i.e. healthy volunteer subjects in Part B, or systemic amyloidosis patients with known cardiac involvement Part C.

Furthermore, a clinically concerning arrhythmia is an adverse event which is deemed by the Investigator in consultation with the Medical Monitor to be of sufficient temporal duration and / or character to potentially affect subject safety.

Detection of the following during baseline assessment or following administration of GSK3039294 will lead to withdrawal:

- a).** Sustained (≥ 10 beats) / symptomatic monomorphic ventricular tachycardia (VT), or rapid polymorphic VT; **b).** Complete heart block; **c).** Brady arrhythmias deemed

clinically concerning by the Investigator in consultation with the Medical Monitor (i.e. *except* physiological bradycardia or first degree heart block).

[figure not shown]
Additional cardiac arrhythmic events could include, but are not restricted, to:

- A sustained arrhythmia (i.e. ≥ 30 seconds) *except* physiological bradycardia.
- A non-sustained wide-complex tachyarrhythmia ≥ 100 / minute that is:
 - accompanied by symptoms or other new ECG changes (e.g. new ST depression)
 - repetitive (e.g. repeated short salvos)
 - Greater than 10 seconds in duration

Subjects who either have a clinically concerning arrhythmic event during the study, or where there is electrophysiological diagnostic uncertainty on cardiac telemetry / ECG, must be withdrawn from the study, and should have an immediate cardiac troponin level evaluated using a high-sensitivity point-of-care assay as outlined in **Section 7.3.7** & **Figure 5**, below.

Affected subjects should be referred to the local cardiology service and the Medical Monitor should be informed as soon as possible.

Figure 5 Algorithm for Management of Subjects having received one or more doses of GSK3039294 in Parts B & C based on Arrhythmia Characterization

In Part C, the patient's amyloidosis physician should be informed as soon as possible after any type of cardiac adverse event, by the Medical Monitor, irrespective of the patient's cardiac amyloid status at Screening.

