5.2. Exclusion Criteria

A subject will not be eligible for inclusion in this study if any of the following criteria apply:

All Subjects

[1] CONCOMITANT MEDICATIONS

1. Use of prohibited medication (Section 6.11.2)

[2] RELEVANT HABITS

1. History of regular alcohol consumption within 6 months of the study defined as:
 - For UK sites – healthy volunteers: an average weekly intake of >21 units for males or >14 units for females. One unit is equivalent to 8 g of alcohol: a half-pint (~240 mL) of beer, 1 glass (125 mL) of wine or 1 (25 mL) measure of spirits.

[3] CONTRAINDICATIONS

1. History of sensitivity to any of the study medications, or metabolite thereof or a history of drug or other allergy that, in the opinion of the investigator or Medical Monitor, contraindicates their participation

[4] DIAGNOSTIC ASSESSMENTS AND OTHER CRITERIA

1. **Cohort 3 (Part B) subjects only:** Cardiac arrhythmia detected on the 48hr screening Holter, with the exception of physiological bradycardia, first-degree heart block, supraventricular premature complexes and / or premature ventricular complexes (PVCs) less than a single 5-beat AIVR
2. **Cohort 3 (Part B) subjects only:** High sensitivity Cardiac Troponin level at screening > ULN for the specified assay
3. Presence of hepatitis B surface antigen (HBsAg), positive hepatitis C antibody test result at screening or within 3 months prior to first dose of study treatment.

4. A positive pre-study drug/alcohol screen (unless a positive test is due to prescribed medications)
5. A positive test for HIV antibody
6. Where participation in the study would result in donation of blood or blood products in excess of 500 mL within 84 days
7. The subject has participated in a clinical trial and has received an investigational product within the following time period prior to the first dosing day in the current study: 30 days, 5 half-lives or twice the duration of the biological effect of the investigational product (whichever is longer). Prior to Part A for subjects participating in Parts A and B
8. Exposure to more than four new chemical entities within 12 months prior to the first dosing day
9. Lactating females
10. Poor or unsuitable venous access

Additional Exclusion Criteria – Healthy Volunteer

[1] CONCURRENT CONDITIONS/MEDICAL HISTORY (INCLUDES LIVER FUNCTION AND QTc INTERVAL)

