7.1.2. Part B – Cohort 3, 7 day repeat dose healthy volunteer subjects

Procedure	Screening (within 28 days of Day 1)	Treatment Period (Days)										Follow-up (7-14 days following last dose)	Notes
		- 2	- 1	1	2	3	4	5	6	7	8		
Outpatient Visit	X											X	
Admission to Clinical Unit		X											
Inpatient Stay at Clinical Unit				←----->									
Informed consent	X												
Inclusion and exclusion criteria	X	X											
Demography	X												
Full physical exam incl height and weight	X												
Brief Physical		X										X	
Medical history (includes substance usage)	X												Substances: Drugs, Alcohol, tobacco and caffeine
Past and current medical conditions	X												
FSH and oestradiol (women)	X												
Clinical Safety Laboratory Assessments (HIV, Hep B and Hep C Screen at screening only ¹) – except Core Urine Monitoring Assessments	X	X			X			X			X	X	On dosing days, samples to be taken in the morning pre-dose. ¹ If performed within 3 months prior to first dose of study treatment, testing at screening is not required.
Clinical Chemistry Only				X		X							
High-sensitivity cardiac Troponin	X			X									Pre-dose
Core Urine Monitoring Assessments	X		X	X		X		X			X	X	Samples for Urine pH to be taken in the morning
Urine Sample (for storage)			X										
Urine Drug/Alcohol Breath Test	X	X											
12-lead ECG and vital signs	X		X	X	X	X	X	X	X	X	X	X	Triplicate for all. Pre-dose and 1hr post-dose
48hr Holter	X												

Procedure	Screening (within 28 days of Day 1)	Treatment Period (Days)										Follow-up (7-14 days following last dose)	Notes
		-2	-1	1	2	3	4	5	6	7	8		
Telemetry		←-----→											Temporary removal of telemetry (e.g. for showering) is permitted
Evaluation of Food Effect							X	X					Fasted on Day 4, Fed on Day 5. Not to be performed in sentinel subjects.
Study Treatment		←-----→											
Blood Sampling (PK)					For sampling time points, see Section 7.4.1							X	For 1st dose and escalation See Section 7.4.1.
Blood Sampling (PD)					For sampling time points, see Section 7.5							X	
Discharge from Clinical Unit											X		Following completion of all assessments
PGx Sample		X											Pre-dose if possible. Informed consent for optional genetics research must be obtained before collecting a sample
AE/SAE review		←-----→										X	
Concomitant medication review	X	←-----→										X	

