7.1.3. Part B – Cohort 4, 21 day repeat dose healthy volunteer subjects

Procedure	Screening (within 28 days of Day 1)	Treatment Period (Days)																					Follow-up (7-14 days following last dose)	Notes					
		- 1	1	2	3	4	5	6	7	8	9	10	11	12	1 3	14	15	1 6	1 7	18	1 9	2 0			21				
Outpatient Visit	X																X ²							X	X	² Visit day ± 2 days is allowed			
Admission to Clinical Unit		X																											
Inpatient Stay at Clinical Unit			←-----→																										
Informed consent	X																												
Inclusion and exclusion criteria	X	X																											
Demography	X																												
Full physical exam incl height and weight	X																												
Brief Physical		X																									X		
Medical history (includes substance usage)	X																											Substances: [Drugs, Alcohol, tobacco and caffeine]	
Past and current medical conditions	X																												
SH and oestradiol (women)	X																							X					

Procedure	Screening (within 28 days of Day 1)	Treatment Period (Days)																					Follow-up (7-14 days following last dose)	Notes
		- 1	1	2	3	4	5	6	7	8	9	10	11	12	1 3	14	15	1 6	1 7	18	1 9	2 0		
Clinical Safety Laboratory Assessments (HIV, Hep B and Hep C Screen at screening only ¹) – except Core Urine Monitoring Assessments	X	X		X			X		X								X ²					X	X	On dosing days, samples to be taken in the morning pre-dose. ¹ If performed within 3 months prior to first dose of study treatment, testing at screening is not required. ² Visit day ± 2 days is allowed
Clinical Chemistry Only			X		X																			
Core Urine Monitoring Assessments	X	X	X		X		X		X								X ²					X	X	Samples for Urine pH to be taken in the morning. ² Visit day ± 2 days is allowed
Urine Sample (for storage)		X																						
Urine Drug/Alcohol Breath Test	X	X																				X		
12-lead ECG and vital signs	X	X	X	X	X	X	X	X	X								X ²					X	X	Triplicate for all. Pre-dose and 1hr post-dose. ² Visit day ± 2 days is allowed
Home Dosing Record										←-----→														

7.1.4. Part B – Cohort 4, 21 day repeat dose healthy volunteer subjects – dose alteration (only if dose alteration is required)

Should a dose alteration be required, subjects will be re-admitted to the clinical unit and the procedures be administered as stated below.
Note: The ‘Dose Day’ relates to the first day of the adjusted dose, and not the study day.

Procedure	Dose Days								Notes
	-1	1	2	3	4	5	6	7	

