7.3.6. Clinical Safety Laboratory Assessments

All protocol required laboratory assessments, as defined in [Table 7](#), must be conducted in accordance with the Laboratory Manual, and Protocol Time and Events Schedule. Laboratory requisition forms must be completed and samples must be clearly labelled with the subject number, protocol number, site/centre number, and visit date. Details for the preparation and shipment of samples will be provided by the laboratory and are detailed in the SRM. Reference ranges for all safety parameters will be provided to the site by the laboratory responsible for the assessments.

If additional non-protocol specified laboratory assessments are performed at the institution's local laboratory and result in a change in subject management or are considered clinically significant by the investigator (e.g., SAE or AE or dose modification) the results must be recorded in the CRF.

Refer to the SRM for appropriate processing and handling of samples to avoid duplicate and/or additional blood draws.

Haematology, clinical chemistry, urinalysis and additional parameters to be tested are listed in [Table 7](#).

Table 7 Protocol Required Clinical Safety Laboratory Assessments

Laboratory Assessments	Parameters			
Haematology	Platelet Count	RBC Indices:	WBC count with Differential:	
	RBC Count	MCV	Neutrophils	
	Hemoglobin	MCH	Lymphocytes	
	Hematocrit		Monocytes	
	Prothrombin Time		Eosinophils	
			Basophils	
Clinical Chemistry ¹	BUN	Potassium	AST (SGOT)	Total and direct bilirubin
	Creatinine	Sodium	ALT (SGPT)	Total Protein
	Glucose	Calcium	Alkaline phosphatase	Albumin
	Phosphate	Bicarbonate		
Routine Urinalysis	
 • Specific gravity • pH, glucose, protein, blood and ketones by dipstick • Microscopic examination (if blood or protein in healthy subjects is abnormal) 			
Core Urine Monitoring Assessments	
 • Spot UPC ratio • Glycosuria using dipstix • Urine pH using a pH meter 			
Other Screening Tests	
 • HIV • Hepatitis B (HBsAg) • Hepatitis C (Hep C antibody) • FSH and estradiol (as needed in women of non-child bearing potential only) • Alcohol and drug screen (to include at minimum: amphetamines, barbiturates, cocaine, opiates, cannabinoids and benzodiazepines) 			

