
NOTES :
 
 1. Details of Liver Chemistry Stopping Criteria and Required Actions and Follow-Up Assessments after liver stopping or monitoring event are given in Section 6 and Appendix 2 2. Local urine testing will be standard for the protocol unless serum testing is required by local regulation or ethics committee. 				

7.3.7. High Sensitivity Cardiac Troponin-T (hs-cTnT) Monitoring after a Cardiac Arrhythmia in Part B, or Part C

Baseline hs-cTnT: In Part B and Part C, all subjects will have hs-cTn level for purposes of screening as well as to provide baseline with which to compare, in the event that a subject develops a clinically concerning cardiac arrhythmic event after dosing with GSK3039294.

Subjects should be advised by the local study site to abstain from strenuous exercise (e.g. running or gym work) ≤ 24 hours before a baseline hs-cTn level is taken.

Monitoring of hs-cTnT after an Arrhythmia Event: A blood samples for hs-cTnT will be taken immediately at the time of onset of a cardiac arrhythmia which is deemed by the Investigator to be of clinical concern (see Section 5.4.4), or where there is electrophysiological diagnostic uncertainty.

High-sensitivity cTn levels should be serially repeated (using the same assay) following local troponin monitoring protocols at the study site, and with advice from a cardiologist if this is deemed clinically necessary by the Investigator.

Additional investigations, including but not restricted to serial ECGs and evaluation of cardiac function using echocardiogram and / or cardiac magnetic resonance (CMR) imaging, can be performed at the discretion of the Investigator in consultation with the Medical Monitor and a cardiologist.

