- **Healthy Subjects:** During each treatment period, subjects will abstain from alcohol for 24 hours (**48 hours for Cohort 3**) prior to the start of dosing until collection of the final PK sample for each in-house session. Subjects will also abstain from alcohol for 24 hours prior to screening and follow-up. At all other times during the study, male subjects should have no more than 2 drinks per day and female subjects should have no more than 1 drink per day (1 drink is equivalent to 12 g of alcohol: 360 mL of beer, 150 mL of wine or 45 mL of 80 proof distilled spirits).

Section 7.1. Time and Events Tables

Changes to assessments for Cohorts 3 and 5 and associated endnotes / footnotes

Section 7.3.5. Cardiac Monitoring – Electrocardiogram (ECG), Telemetry & Non-Implantable Devices for Remote Monitoring

PREVIOUS TEXT

- 12-lead ECGs will be measured in semi-supine position after 5 minutes rest (triplicate readings will be taken and averaged at all times) will be obtained at each timepoint during the study using an ECG machine that automatically calculates the heart rate and measures PR, QRS, QT, and QTcF intervals. Refer to Section 5.4.3 for QTcF withdrawal criteria and additional QTcF readings that may be necessary.
- Continuous ambulatory cardiac telemetry will be performed from 12hrs pre-dose to 72 hours post-dose of GSK3039294 in systemic amyloidosis patients with known cardiac involvement during Part C, and thereafter, at any time during any part of the study, at the investigator's discretion. Full disclosures will be reviewed in detail and the review maintained as part of the subject's source documents.

REVISED TEXT

- 12-lead ECGs will be measured in semi-supine position after 5 minutes rest (triplicate readings will be taken and averaged at all times) will be obtained at each timepoint during the study using an ECG machine that automatically calculates the heart rate and measures PR, QRS, QT, and QTcF intervals. Refer to Section 5.4.3 for QTcF withdrawal criteria and additional QTcF readings that may be necessary.
- ~~Continuous ambulatory cardiac telemetry will be performed from 12hrs pre-dose to 72 hours post-dose of GSK3039294 in systemic amyloidosis patients with known cardiac involvement during Part C, and thereafter, at any time during any part of the study, at the investigator's discretion. Full disclosures will be reviewed in detail and the review maintained as part of the subject's source documents.~~

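### Section 7.3.7 promises a baseline troponin to all Part B and Part C subjects, but the Cohort 4 schedule shows none

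*Protocol*

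**What the plan says.** Section 5.4.4 sets the action after an arrhythmia on treatment. A subject whose event is clinically concerning, or whose tracing leaves the diagnosis uncertain, "must be withdrawn from the study, and should have an immediate cardiac troponin level evaluated using a high-sensitivity point-of-care assay". The risk table in 4.6.1 gives the purpose of that sample: to rule out myocardial ischaemia or injury linked to the arrhythmia.

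Section 7.3.7 provides the value to compare it with: "In Part B and Part C, all subjects will have hs-cTn level for purposes of screening as well as to provide baseline". The comparison is to be made "in the event that a subject develops a clinically concerning cardiac arrhythmic event after dosing with GSK3039294". The sentence has no cohort restriction, and Cohort 4 (4a and optional 4b) is part of Part B under 4.2.2.

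The schedules are in section 7.1. Table 7.1.2 for Cohort 3 has a row "High-sensitivity cardiac Troponin", marked at Screening and Day 1 pre-dose. Table 7.1.5 for Cohort 5 has the same row, marked at Screening and Day 1. Table 7.1.3, "Cohort 4, 21 day repeat dose healthy volunteer subjects", shows no such row. The opening of section 7 refers to these tables for the exact timing of each assessment and makes adherence to them a requirement.

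**The concern.** The text and the schedule disagree about whether Cohort 4 has a baseline troponin, and at the bedside the schedule is what the site follows. A site working from 7.1.3 would not draw the sample that 7.3.7 relies on.

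If a Cohort 4 volunteer then had a clinically concerning arrhythmia, the immediate troponin would have nothing pre-dose beside it. Serial samples would show how the level moved after the event, but not whether it was already raised before dosing. Entry screening does not close the gap, because the criterion in 5.2, "High sensitivity Cardiac Troponin level at screening > ULN for the specified assay", applies to Cohort 3 only. Cohort 4 is the study's first 21-day exposure, and under 4.2.3 its safety review decides whether Part C opens, so an unreadable result there would reach a go/no-go decision.

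**Working it through.** This is a cross-check of text against schedule. The plan gives no figure to reproduce, and nothing depends on power or error rates.

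**Step 1. Who is promised a baseline, and who has one scheduled**

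| Cohort | Part | Promised by 7.3.7 | Troponin row in 7.1 | Planned number |
|---|---|---|---|---|
| 3 | B | yes | yes: Screening, Day 1 pre-dose (7.1.2) | at least 6 |
| 4a | B | yes | none shown (7.1.3) | at least 6 |
| 4b (optional) | B | yes | none shown (7.1.3) | at least 6 |
| 5 | C | yes | yes: Screening, Day 1 (7.1.5) | at least 12 |

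The numbers are the planned completers in 4.2.2 and the enrolment minimum in 4.3.

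**Step 2. Is the Cohort 4 row missing from the plan or only from the copy?**

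The Cohort 4 table ends after the home dosing record. Rows that the other tables go on to give, such as study treatment, blood sampling and adverse event review, are not there, so absence alone is weak evidence. Two things make a lost row unlikely:

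- In the Cohort 3 and Cohort 5 tables, troponin stands between the chemistry-only row and the core urine monitoring row. Both of those rows survive in the Cohort 4 table, next to each other, with nothing between them.
- The Appendix 5 entry for the amendment that added 7.3.7 describes the schedule revision as "Changes to assessments for Cohorts 3 and 5 and associated endnotes / footnotes". Cohort 4 is not named. This is corroboration only; the contradiction is between two pieces of current text.

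Table 7 in 7.3.6, "Protocol Required Clinical Safety Laboratory Assessments", does not help either way. It omits troponin for every cohort, including the two that have it scheduled.

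**Step 3. Size**

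- Promised a baseline with none scheduled: 6 (4a), or 6 + 6 = 12 with 4b. These are minima.
- Samples needed to close the gap, at Screening and Day 1 pre-dose: 2 × 6 = 12 for 4a; 2 × 12 = 24 with 4b.

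**Step 4. A related wording point in 5.4.4**

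The definition of a clinically concerning arrhythmia refers to normal variation for each type of subject on repeat dosing. Its i.e. clause then names Part B volunteers and only those Part C patients whose heart is known to be involved. Part C also takes patients without known cardiac involvement, starting with the renal sentinel in 4.2.3.1. The action sentence in the same section has no such limit, and the Figure 5 title covers anyone dosed at least once in Parts B and C. The clause is narrower than the rule it explains.

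**The case against.** The strongest reply is that the schedule is right and 7.3.7 is loosely worded. The amendment that introduced the section was meant to increase cardiac monitoring in Cohorts 3 and 5, so Part B may have been written where Cohort 3 was meant. That is plausible, and it bears on which text to correct. It does not remove the contradiction, because the current sentence covers all of Part B.

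A second reply is that the truncated table may hide the row, and that row order is not constant across tables (the brief physical examination moves in Cohort 5). This keeps the finding short of certain. A check of the complete table would settle it.

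A third is that the consequence is small: withdrawal does not wait for the troponin result, and 7.3.7 already provides for serial repeats on the same assay, with cardiology advice and imaging where needed. This stands. It limits the loss to interpretation of the result.

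A reader might go further and infer that the arrhythmia stopping rule does not cover Cohort 4, or leaves Part C patients without known cardiac involvement unprotected. The documents do not support either. A laboratory schedule does not set the population of a stopping rule. The action sentence in 5.4.4, the Figure 5 title and the 7.3.7 heading all extend to Parts B and C. The listed withdrawal arrhythmias, the diagnostic-uncertainty trigger and investigator discretion are not limited by cardiac status, and the Cohort 5 troponin row applies to all its patients. The i.e. clause costs consistency and no identified protection.

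**Conclusion.** The contradiction stands. Section 7.3.7 promises a baseline that the Cohort 4 schedule, as far as it can be read, does not provide. At least 6 volunteers in 4a, or 12 with 4b, would lack the comparator for the troponin required by 5.4.4. This rests on the planned minimum cohort sizes and on the Cohort 4 table having no troponin row after the point where it breaks off; confidence is medium for that reason. It is a modest, cheaply corrected safety-monitoring defect with no effect on sample size or analyses.

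Two further inferences should be resisted. The gap should not be scaled by the doses in Table 5 of section 4.5: those are examples, they do not measure a missing baseline, and the protocol gives no arrhythmia rate on repeat dosing. Nor does the point justify making an arrhythmia clinically concerning regardless of attribution. That would be a new withdrawal rule, and it sits badly with the stated aim in 7.3.5.2 of limiting false attribution to the drug in cardiac amyloid patients.

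**What to change.** First confirm against the complete 7.1.3 table that it has no troponin row. Then make the two places agree:

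- Preferred: add high-sensitivity troponin at Screening and Day 1 pre-dose to 7.1.3, as in Cohort 3. The cost is two samples per subject at visits already planned, 12 for 4a and 24 with 4b, and no new visits.
- If the sponsor did not intend a Cohort 4 baseline, restrict the baseline sentence in 7.3.7 to Cohorts 3 and 5. This costs only wording, but accepts that a Cohort 4 event would be read without a pre-dose value.

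As a minor alignment in the same revision, let the i.e. clause in 5.4.4 name Part C patients with or without known cardiac involvement, to match the action sentence and the Figure 5 title. The attribution wording in 5.4.4 can stay as it is.
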